19.2.2 Safety Variables

The assessments at the Withdrawal Visit and Unscheduled Visits (assessments not recorded at a scheduled visit) will be assigned to a nominal visit according to the visit windowing specified in [Panel 8](#), [Panel 9](#) and [Panel 10](#). Note, assessments after Visit 2 for enrolled patients that did not have any IMP intake will be assigned to nominal Visit 2.

In analyses of vital signs parameters using visit, if the Withdrawal Visit is assigned to the same visit as a scheduled visit, the assessment at the Scheduled Visit will be used.

For 16159A-patients, additional ECG assessments will be performed if the daily dosing is switched to weekly dosing. These assessments will not be windowed.

Panel 8 Visit Windows: Vital Signs

Nominal Visit Number	Nominal Visit Week	Nominal Visit Day	Time Window
V2 (Baseline Visit)	0	0	NA
V3	1	7	Day after first IMP – 11
V4	2	14	12-21
V5	4	28	22-35
V6	8	56	49-63
V7	12	84	77-91
V8	16	112	105-119
V9	20	140	133-147
V10	24	168	161-175
V11	28	196	189-203
V12	32	224	217-231
V13	36	252	245-259
V14	40	280	273-287
V15	44	308	301-315
V16	48	336	329-343
V17 (Primary Outcome/Withdrawal Visit)	52	364	>357

Panel 9 Visit Windows: Laboratory Tests, Body weight, and Waist circumference

Nominal Visit Number	Nominal Visit Week	Nominal Visit Day	Time Window
V2 (Baseline Visit)	0	0	NA
V5	4	28	22-35
V10	24	168	161-175
V17 (Primary Outcome/Withdrawal Visit)	52	364	>357

Panel 10 Visit Windows: ECG

Nominal Visit Number	Nominal Visit Week	Nominal Visit Day	Time Window
V2 (Baseline Visit)	0	0	NA
V5	4	28	22-35
V8	16	112	105-119
V11	28	196	189-203
V14	40	280	273-287
V17 (Primary Outcome/Withdrawal Visit)	52	364	>357

Note that if the first IMP in the Treatment Period is the same day as the assessment, the assessment is assumed to be before the IMP intake.

Laboratory tests for which fasting is relevant (blood and serum tests for CDISC terms CHOL, GLUC, HDL, LDL, and TRIG) will have separate PARAM values in ADaM data, one for fasting and one for non-fasting/unknown, and fasting and non-fasting/unknown assessments will be considered separately.

The Baseline value will be the last assessment at or before Visit 2. If there is more than one assessment at the day of the last assessment, they will be ordered after date and time where assessment without recorded time will be considered to come after assessments recorded with time. The assessment last in the ordering will be used. If there is more than one assessment on the same date (and time), e.g. two assessments on the same date without recorded time, the maximum value will be used.

For last post-baseline assessments in the Treatment Period, the same ordering rule will be used as for Baseline.

In analyses using visit, if there is more than one assessment at a nominal visit, the value will be selected using the following prioritization rule:

1. Scheduled Visit

If there is more than one assessment recorded at a scheduled visit, the one closest to the nominal day for the visit will be used in analyses using visit. If there are more than one assessment that are equally close to the nominal day, they will be ordered after date and time where assessments without recorded time will be considered to come after

assessments recorded with time. The assessment first in the ordering will be used. If there is more than one assessment on the same date (and time), the maximum value will be used.

2. Withdrawal Visit or Unscheduled Visit

If there is more than one assessment, the value for analyses using visit will be selected using the same ranking as for multiple assessments at scheduled visits.

19.3 Handling Missing or Incomplete Dates/Times

19.3.1 IMP Start and Stop Dates

A missing IMP start date will be imputed with the date of Visit 2.

A missing IMP stop date will not be imputed.

Exposure and compliance will not be calculated for patients with missing IMP start-or-stop dates. Thus, a patient with a missing IMP start-or-stop date will contribute as having no exposure in the calculation of PYE. This also holds for patients not receiving any IMP.

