4.2 Exploratory Endpoints

- Exploratory safety and tolerability endpoints:
 - Change from baseline in AIMS, BARS Global Clinical Assessment of Akathisia score (item 4) score and mSAS total score
 - C-SSRS
- Exploratory efficacy endpoints:
 - *Psychotic symptoms*
 - Change from baseline in PANSS total score
 - Change from baseline in PANSS subscale scores (PANSS Negative Symptoms subscale, PANSS Positive Symptoms subscale, PANSS General Psychopathology subscale)
 - *Negative symptoms*
 - Change from baseline in NSA-4 total score
 - Change from baseline in PANSS Marder factor score (negative symptoms)
 - *Global clinical impression*
 - Mean change from baseline in CGI-S score
 - *Andreasen symptoms remission*
 - Remission (simultaneous ratings of mild or less on PANSS specific items: P1, G9, P3, P2, G5, N1, N4, and N6) at Week 52 Visit
 - *Quality of life and functioning*
 - Change from baseline in QLS score
 - Change from baseline in ToolL score
 - Change from baseline in WorQ score
 - Change from baseline in PSP total score
 - *Treatment satisfaction*
 - Change from baseline in MSQ score
 - Health care resource used during the 52-week study period

5 Analysis Sets

The patients will be assigned to analysis sets based on IMP intake and post-baseline assessments of the efficacy variable(s) in the Treatment Period.

Due to a higher-than-anticipated roll-over rate and a lower-than-anticipated attrition rate from study 16159A, only patients from study 16159A and 16323A are enrolled in the study, i.e. no patients who have not previously participated in a study investigating Lu AF35700 are enrolled.

Only 4 patients from study 16323A are enrolled. Therefore, data from these will only be presented in listings, i.e. they will not contribute to any summary tables.

The sets of patients to be analysed are defined as follows:

- *all-patients-enrolled set* (APES) – all patients enrolled, including patients from study 16323A
- *all-patients-treated set* (APTS) – all patients from study 16159A who took at least one dose of Lu AF35700 in study 16159B
- *full-analysis set* (FAS) – all patients in the APTS (i.e. only patients from study 16159A are included) who had a valid baseline assessment and at least one valid post baseline assessment of PANSS total score in study 16159B.

Since this is an open-label study each patient will be classified according to these definitions based on information in data and no Classification Meeting will be held.

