Recent and concomitant medication will be coded using the *WHO Drug Dictionary* (WHO-DDE).

Medications will be classified according to the start and stop time and summarized by anatomical therapeutic chemical (ATC) code levels 2 and 3, generic drug name, previous treatment group, and for each of the categories:

- Medication started before first dose of IMP (i.e. on-going concomitant medication from the lead-in study) and continued after first dose of IMP
- Concomitant medication started at or after first dose of IMP

The tables will be based on the APTS.

10 Exposure and Compliance

Exposure (days) to IMP in study 16159B will be calculated as:

$$\text{Last date of IMP} - \text{Start date of IMP} + 1$$

For details about handling of missing IMP start or stop date, see section 19.3.1 (IMP Start and Stop Dates).

The exposure for patients on the weekly dosing regimen will be summarized together with the exposure for patients on the daily dosing regimens.

Exposure to IMP will be summarized overall and by previous treatment group using descriptive statistics, and summaries will include the patient years of exposure (PYE). PYE will be calculated as the sum of the number of days of exposure to IMP for each patient, divided by 365.25 days.

In addition, exposure to IMP will be categorized in intervals 1 – 84 days [0 – 3 months], 85 – 168 days [3 – 6 months], 169 – 252 days [6 – 9 months], 253 – 336 days [9 – 12 months], > 336 days [>12 months], and summarized overall and by previous treatment group.

The final dose level for patients in APTS will be summarized overall and by previous treatment group.

The number of patients switching to the weekly dosing regimen will be summarized based on the APTS. The summary will include the number of patients going back to daily dosing after initiating weekly dosing.

Non-compliant days are days on which no IMP has been taken, less than the full dose of IMP has been taken, or more than the full dose of IMP has been taken.

Compliance (%) with IMP for the Treatment Period will be calculated as:

$$\frac{\text{Last date of IMP} - \text{Start date of IMP} + 1 - \text{Number of non-compliant days}}{\text{Last date of IMP} - \text{Start date of IMP} + 1} \times 100$$

where the number of non-compliant days is defined as the sum of all non-compliant days from the start of the interval to the end of the interval.

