12.1.2 Classification of Adverse Events

Adverse events will be classified according to the time of onset of the adverse event (for handling of incomplete start dates, see section 19.3.5):

- *pre-study adverse event* – an adverse event that starts before the date of first dose of IMP in study 16159B.
- *treatment-emergent adverse event (TEAE)* – an adverse event that starts, increases in intensity compared to the preceding intensity, or changes from non-serious to serious on or after the date of first dose of IMP in study 16159B.

Handling of adverse events that increase in intensity or seriousness is further specified in section 19.4.2.

An adverse event is considered causally related to the use of the IMP when the causality assessment by the investigator is *probable* or *possible*.

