12.1.5 Presentation of Adverse Events

All adverse events will be listed for the APES, including a flag for TEAEs. A listing of all AEs occurring while on weekly dosing will also be presented.

An overview of the PYE, number and percentages of patients with TEAEs, serious adverse events (SAEs), TEAEs leading to withdrawal, and of patients who died will be provided based on the APTS. For TEAEs, SAEs, and adverse events leading to withdrawal, the total number of events will be included.

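### SAP 19.3.1 leaves treated patients with a missing IMP start or stop date out of patient-years of exposure while their adverse events still count, so PYE is understated whenever such a date is missing

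*SAP*

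**What the plan says.** SAP section 10 (Exposure and Compliance) takes exposure as last IMP date minus first IMP date plus one, and states: "PYE will be calculated as the sum of the number of days of exposure to IMP for each patient, divided by 365.25 days". For missing dates it refers to section 19.3.1, which contains four rules:

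- Start date: "A missing IMP start date will be imputed with the date of Visit 2".
- Stop date: "A missing IMP stop date will not be imputed".
- Exposure: "Exposure and compliance will not be calculated for patients with missing IMP start-or-stop dates".
- PYE: "a patient with a missing IMP start-or-stop date will contribute as having no exposure in the calculation of PYE". The section then applies the same treatment to patients who received no IMP.

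SAP section 5 (Analysis Sets) defines the APTS as "all patients from study 16159A who took at least one dose of Lu AF35700 in study 16159B". It does not require complete IMP dates.

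SAP 12.1.2 ties treatment-emergent status to the first dose only: an event qualifies if it starts, worsens in intensity or "changes from non-serious to serious on or after the date of first dose of IMP in study 16159B".

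SAP 12.1.5 plans one APTS table that opens with "An overview of the PYE, number and percentages of patients with TEAEs" and goes on to serious events, withdrawals due to events, deaths and total numbers of events.

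**The concern.** The exposure total and the event counts in the 12.1.5 overview are meant to describe the same patients, but the two follow different inclusion rules. One dose is enough for a patient's events to count. Both IMP dates are needed for that patient's time to count. A patient with months of visits and returned drug but no recorded stop date therefore adds events and no exposure, exactly like someone who never took a tablet.

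The primary objective is long-term safety, and SAP section 16 justifies the study's size by the long-term safety information it will give. PYE is the summary of how much treatment time stands behind that information, and a reader who wants an event rate will divide by it. The same patients also have no calculated exposure for the duration categories and no calculated compliance.

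**Working it through.** The documents state no PYE total and no number of missing dates, so there is no figure to reproduce. The check has two parts.

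**1. Does anything restore the lost time or remove the events?**

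- Events in: APTS membership needs one dose (SAP section 5). Treatment-emergent status needs the first-dose date (12.1.2), and a missing one is replaced by the Visit 2 date (19.3.1). The Treatment Period for events ends at the Primary Outcome/Withdrawal Visit (12.1.4), not at the IMP stop date, and follow-up events are folded into the same summaries (12.1.1). No step needs the stop date.
- Time out: section 10 sends missing dates to 19.3.1, and 19.3.1 drops the patient from the sum. No other section puts the days back.
- Start date: section 7.2 cites 19.3.1 and uses the imputed start date for Kaplan-Meier time to withdrawal. The same patient thus has time on treatment in that plot and none in PYE.

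**2. How large is the shortfall?**

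With m treated patients lacking a date and d true days on IMP each, loss in PYE = m × d / 365.25.

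Maximum per patient, for the full 52 weeks: 364 / 365.25 = 0.997 patient-years.

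For a relative size a base is needed. Inputs:

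- N = 500. SAP section 16 says more than 500; 500 is used for illustration.
- 50% completion, from the 200 completers of 400 enrolled planned in Protocol 5.1. Carrying it over to this population is an assumption.
- Time to withdrawal: assumed.

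Base A, withdrawals averaging 182 days: 500 × (0.5 × 364 + 0.5 × 182) / 365.25 = 373.7 PYE.

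Base B, constant withdrawal hazard reaching 50% at one year: mean exposure 0.5 / ln 2 = 0.72 year, and 500 × 0.72 is about 361 PYE.

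Loss on base A, in patient-years (% of PYE):

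| m | d = 28 days | d = 182 days | d = 364 days |
|---|---|---|---|
| 0 | 0 | 0 | 0 |
| 5 | 0.38 (0.1%) | 2.49 (0.7%) | 4.98 (1.3%) |
| 10 | 0.77 (0.2%) | 4.98 (1.3%) | 9.97 (2.7%) |
| 25 | 1.92 (0.5%) | 12.46 (3.3%) | 24.91 (6.7%) |
| 50 | 3.83 (1.0%) | 24.91 (6.7%) | 49.83 (13.3%) |

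On base B with 0.5 year per affected patient:

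- 15 patients (3%): 15 × 0.5 = 7.5; 7.5 / 361 = 2.1%.
- 25 patients (5%): 25 × 0.5 = 12.5; 12.5 / 361 = 3.5%.

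If 90% complete, base A becomes 473.4 PYE and 25 patients cost 0.4% to 5.3% over the same range of d.

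A rate derived by a reader would be too high by the factor true PYE / reported PYE. For 25 patients at 182 days on the 50% base this is 373.7 / (373.7 − 12.46) = 1.034, or about 3.4% too high.

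**The case against.** The strongest reply is that no planned result uses PYE as a denominator. SAP 12.1.1 specifies numbers and percentages of patients with an event, the 12.1.5 overview sets PYE beside counts, and PYE is not a primary endpoint. That stands. A reader might infer that the planned adverse event incidences are biased, but the documents do not support this: their denominators are patients.

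Second, the direction is conservative. Less claimed exposure and a higher derived rate cannot hide a risk. That also stands, and it limits the importance of the point.

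Third, a reader might say that 19.3.1 contradicts itself by imputing a start date and then ignoring it. That is too strong. The imputed date has uses outside exposure, in time to withdrawal (7.2) and in classifying events (12.1.2). What remains is an inconsistency across analyses.

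Fourth, a reader might infer that zero days enter the exposure mean, median or duration categories. The text says exposure is not calculated for these patients. They are omitted from those summaries, and the no-exposure statement concerns PYE only. Since continuous summaries show n (section 6), a shortfall against the APTS should be visible, but that does not correct the total.

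Fifth, missing dates may be rare. Protocol Panel 2 schedules IMP return and accountability from Week 1 to Week 52, Protocol 6.5 requires a patient-specific log, and the eCRF has entry checks. The number could be zero. However, the same records show that a better value than none is usually available.

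Finally, any imputed stop date is approximate, because dispensing does not prove intake. That is true, and it is a reason to fix one rule in advance and show its effect. It does not make omission accurate for a patient known to have taken the drug.

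**Conclusion.** The point holds as a defect in a reported descriptive total. Under 19.3.1, PYE is understated whenever at least one treated APTS patient lacks an IMP start or stop date, by at most 0.997 patient-years each, with no matching removal of events.

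The overall size is unknown. The 2% to 3.5% figure is an illustration that rests on 15 to 25 affected patients among 500, about half a year of treatment each and 50% completion; it is not an estimate. A reader might also infer that the loss is selective because stop dates would go missing mainly in patients lost to follow-up. That is plausible, but nothing in the documents shows it, and the conclusion does not depend on it.

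The consequences are confined to the PYE total, the exposure and compliance summaries from which these patients drop out, and any event rate a reader computes from PYE. The point applies to patients from study 16159A; the four from study 16323A appear only in listings. It is worth correcting because the correction is cheap and uses data already collected.

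**What to change.** Amend SAP 19.3.1 as follows:

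- Use the start date imputed with Visit 2 for exposure and PYE as well as for the other analyses.
- Impute a missing stop date with one pre-specified value: the last date on which IMP use is documented (last recorded intake or accountability date), otherwise the last attended Treatment Period visit. Cap it at the withdrawal date when that date is known. The condition is needed because 19.3.2 does not impute missing withdrawal dates.
- Flag imputed start and stop dates, and report how many patients have each.
- Keep zero exposure only for patients who took no IMP.

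The inputs exist: accountability at each visit from Week 1 (Protocol Panel 2), the patient log (Protocol 6.5) and the date of latest intake at pharmacokinetic visits (Protocol 9.3).

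The cost is a few sentences and one small derivation, with no new data collection. The downside is that an imputed stop date is approximate, so the PYE table can also show the total without the imputed patients.

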19.3.2 Withdrawal Date

Missing withdrawal dates will not be imputed and time to withdrawal from treatment will not be calculated for missing withdrawal dates.

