## **5 Study Population**

### **5.1 Numbers of Patients and Sites**

Planned regions:

North America, Europe and South America

Approximately planned number of patients:

to be enrolled:	400
to complete the study:	200

Approximately planned number of:

study sites:	120
--------------	-----

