7.2 Withdrawals

The number of patients who withdrew from treatment will be summarized overall and by previous treatment both by primary reason for withdrawal, and all reasons for withdrawal.

Patients who withdrew from treatment will be listed and the listing will include the reason type (primary or secondary reason for withdrawal from treatment), the reason, specification of other reason, previous treatment group, date of Visit 2, date of withdrawal from treatment, and number of days on IMP in this study. Note that patients can have more than one secondary reason for withdrawal from treatment so the listing will include both the primary reason for withdrawal from treatment and all reasons for withdrawal from treatment.

Kaplan-Meier failure plots of time to withdrawal from treatment will be presented for the total group. The time will be calculated from the date of first dose of IMP in this extension study (for handling of missing IMP start date, see section 19.3.1) to the date of completion or withdrawal from treatment. Patients who completed treatment will be regarded as censored.

All tables and graphs will be based on the APTS. Listings will be based on the APES.

8 Demographics and Baseline Characteristics

Demographics (sex, age, age group, race, and ethnicity); baseline characteristics (height, weight, BMI, and waist circumference); baseline disease characteristics (age – and years since diagnosis of schizophrenia, years since first – and number of antipsychotic treatments, number of psychiatric hospitalizations), social histories; and baseline efficacy variables (PANSS total and subscale scores, CGI-S score, and PSP total score) will be summarized overall and by previous treatment group. CGI-S will be summarized both as a continuous and a categorical variable.

Concurrent as well as relevant past medical, neurological, and psychiatric disorders at the lead-in study Screening Visit will be coded using the *Medical Dictionary for Regulatory Activities* (MedDRA) and summarized.

A concurrent medical, neurological, or psychiatric disorder is a disorder that is ongoing at the Screening Visit of the lead-in study. A past medical, neurological, or psychiatric disorder is a disorder that ended prior to the Screening Visit of the lead-in study.

Demographics and baseline characteristics will be summarized based on the APTS, and baseline efficacy variables will be summarized based on the FAS.

9 Recent and Concomitant Medication

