12.6.2 EPS Rating Scale Scores

For details about data handling, see section [19.1](#), [19.2](#).

Absolute and change from baseline in AIMS total score, mSAS total score, and BARS Global Clinical Assessment of Akathisia score (item 4) will be summarised at by week in the Treatment Period based on the APTS (baseline will also be included in the summaries of the absolute scores). The maximum change from baseline in the Treatment Period will also be summarised.

In addition, the BARS Global Clinical Assessment of Akathisia will be presented with descriptive tables showing number and percentage of patients in each category for baseline and by week in the Treatment Period based on the APTS.

The single-item scores for AIMS items 8 to 12 and BARS items 1 to 4 will be summarized by visit.

13 Pharmacokinetic/Pharmacodynamic Analyses

No pharmacokinetic/pharmacodynamics analyses are planned.

14 Blinded Data Reviews

Not applicable.

15 Interim Analyses

Not applicable.

16 Sample Size Considerations

No formal sample size calculation has been performed for the present study.

As stated in the clinical study protocol, it was expected that approximately 400 patients would be enrolled in the study distributed as follows: 270 from study 16159A, 30 from study 16323A and 100 patients who had not previously participated in a study investigating Lu AF35700. However, the distribution of the number of patients could be adjusted based upon the recruitment rate in each group. As mentioned in section 2, the actual patients recruited were for the most part from study 16159A except for 4 patients from study 16323A.

Since more than 500 patients are included in the study, it will be possible to obtain solid information on long-term safety of Lu AF35700.

To ensure sufficient exposure to the daily dosing regimen, the number of patients who completed study 16159A and who could be treated with the weekly dosing regimen was limited to 50 patients.

17 Statistical Software

The statistical software used will be SAS[®], Version 9.4 or later.

18 Changes to Analyses Specified in the Protocol

Due to the results from the lead-in study 16159A from which the majority of patients come from, the following changes have been made:

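### Withdrawn patients with no withdrawal date cannot enter the Kaplan-Meier withdrawal plot, so any missing date lifts its week-52 retention above the disposition tables

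*SAP*

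**What the plan says.** SAP 7.2 (Withdrawals) plans the display: "Kaplan-Meier failure plots of time to withdrawal from treatment will be presented for the total group". Time runs from first dose in the extension study to completion of, or withdrawal from, treatment. The only censoring rule is "Patients who completed treatment will be regarded as censored". The analysis set is fixed by "All tables and graphs will be based on the APTS".

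SAP 19.3.2 (Withdrawal Date) covers missing dates: "Missing withdrawal dates will not be imputed and time to withdrawal from treatment will not be calculated for missing withdrawal dates". Neither section gives a fallback date, a censoring rule for these patients or a sensitivity display.

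The withdrawal counts do not depend on a date. SAP 7.1 counts completers and withdrawals in the APTS, and 7.2 adds: "The number of patients who withdrew from treatment will be summarized overall and by previous treatment both by primary reason for withdrawal, and all reasons". SAP 3.3 also defines withdrawal from treatment without reference to a date.

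The other end of the same interval is treated differently. SAP 19.3.1 says: "A missing IMP start date will be imputed with the date of Visit 2", and 7.2 refers to that rule for the plot.

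**The concern.** Only a patient who withdrew can lack a withdrawal date. Every patient who loses a time value under 19.3.2 is therefore a known event, while all completers stay in as censored observations. The loss depends on the outcome being plotted.

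Two consequences follow if any dates are missing. The end of the curve shows a smaller withdrawal proportion than the disposition table, with no explanation on the page. The plot would also silently cover fewer patients than the analysis set named for it.

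Missing dates are plausible. Protocol 5.4 defines loss to follow-up by missed visits and failed contact attempts, which supplies no natural date, and Protocol 8.4 asks for a Withdrawal Visit only where one can be arranged. What is at stake is modest: Protocol 3.2 names withdrawal among the means of assessing safety and tolerability, and this curve is the planned picture of how retention develops over the 52 weeks.

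**Working it through.** The documents give no retention estimate or missing-date rate, so there is no planned figure to reproduce.

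**Inputs**
- N = 500, a round figure for illustration. SAP section 16 says: "Since more than 500 patients are included in the study, it will be possible to obtain solid information on long-term safety of Lu AF35700".
- W = 250 withdrawals (50%). Protocol 5.1 plans 400 enrolled and 200 "to complete the study". W = 150 (30%) is a second case.
- m = withdrawals with no date. This is an **assumption**, so a range is shown.
- All completers are censored after the last withdrawal.

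**Week 52.** With everyone included, retention is 1 − W/N. With the m undated patients absent it is 1 − (W − m)/(N − m) = (N − W)/(N − m). This is larger whenever m > 0 and W < N.

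| W | m (share of W) | Retention, all included | Retention on plot | Overstatement (points) |
|---|---|---|---|---|
| 250 | 0 | 50.0% | 250/500 = 50.0% | 0 |
| 250 | 2 (about 1%) | 50.0% | 250/498 = 50.2% | 0.2 |
| 250 | 5 (2%) | 50.0% | 250/495 = 50.5% | 0.5 |
| 250 | 15 (6%) | 50.0% | 250/485 = 51.5% | 1.5 |
| 250 | 25 (10%) | 50.0% | 250/475 = 52.6% | 2.6 |
| 250 | 30 (12%) | 50.0% | 250/470 = 53.2% | 3.2 |
| 150 | 3 (2%) | 70.0% | 350/497 = 70.4% | 0.4 |
| 150 | 15 (10%) | 70.0% | 350/485 = 72.2% | 2.2 |

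**Earlier times.** Let A be the number still on treatment at a given day and a the number of undated patients among them. The plot gives (A − a)/(N − m) instead of A/N. It is too high when a/m < A/N and too low when a/m > A/N. A product-limit calculation on simulated withdrawal days (N = 500, W = 250, m = 25) gives 76.8% at day 168, so A = 384:
- undated patients are the earliest leavers (a = 0): 384/475 = 80.8%, too high;
- undated patients are a random subset (a = 13): 371/475 = 78.1%, too high;
- undated patients are the latest leavers (a = 25): 359/475 = 75.6%, too low.

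In all three cases week 52 reads 52.6% instead of 50.0%.

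**Censoring instead.** If the 25 patients were censored at their true last day, week-52 retention would be 53.6% in the random case, 52.6% if they left earliest and 55.0% if latest. Censoring therefore does not remove the bias.

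**Keeping them as events.** Placing the 25 as events 28 days before their true date (no earlier than day 1) returns week 52 to 50.0%. In the random case the checked earlier points move by 0.6 (day 84: 90.0% to 89.4%), 0.2 (day 168: 76.8% to 76.6%) and 0.8 (day 252: 66.2% to 65.4%).

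**The case against.** The strongest reply is that nothing shows the problem will occur. Protocol 8.4 requires the reason for withdrawal on a form and a prompt Withdrawal Visit, Protocol 11.1.1 provides for automated data entry checks, and the withdrawal date is a field in the 7.2 listing. With no missing dates the bias is zero, and with 1% to 2% missing it is too small to notice on a descriptive plot. This stands, and it limits the size of the point.

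It also stands that the information survives elsewhere. The tables in 7.1 and 7.2 give the correct proportion, the listing would expose an undated withdrawal, and SAP 12.1.9 separately reports adverse events leading to withdrawal. Withdrawal is not among the endpoints in Protocol section 16 or SAP section 4, and no test or decision rule uses the curve.

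A further reply is that the SAP generally declines to compute durations from missing dates: 19.3.1 does so for exposure, and 19.3.4 and 19.3.5 for medications and adverse events. That is a real convention, but it does not settle the matter. The same plot already accepts an imputed start date, and here the omission removes only events.

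A reader might infer that the whole curve overstates retention. The documents do not support that: before week 52 the direction can reverse if the undated patients left late. A reader might also say that the SAP deletes these patients. It does not say so; their absence follows from having no calculated time.

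**Conclusion.** The point holds in a limited form. Under 19.3.2 a known withdrawal with no date has no time value and so drops out of the 7.2 plot, while the tables still count it. If at least one date is missing, week-52 retention on the plot is overstated and disagrees with the tables; at earlier times either direction is possible.

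The size rests on an assumed missing-date rate, together with N = 500 and 50% withdrawing. Over the range from no missing dates to 12% of withdrawals, it runs from zero to 3.2 points. The documents do not show that any date will be missing, and they do not support a claim that the study's reported withdrawal proportion is biased, because the tables are unaffected. This is a minor, inexpensive correction to a descriptive display.

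**What to change.** Amend SAP 19.3.2, for the Kaplan-Meier plot only. Impute a missing withdrawal date with the later of the last documented IMP date and the last attended Treatment Period visit. Use the visit alone if no IMP date is available, since 19.3.1 leaves a missing IMP stop date unimputed. Keep the patient as an event, and footnote the plot with the number of dates imputed.

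The cost is one sentence and one footnote, with no new data. The downside is that some events may be placed slightly early, mainly for patients lost to follow-up. The tables and listings need no change.
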